On the day of the initial visit with administration of venetoclax (Cycle 1 Day 2), serial vital signs, serum chemistry, and hematology samples will be drawn before the dose of venetoclax and at 8 and 24 hours following the dose (see Appendix 1). These samples are to be sent STAT to the laboratory and the investigator or designee must review the results promptly. Laboratory values obtained before the dose of venetoclax are to be used to determine whether a patient developed a change related to TLS. Laboratory results of the 24-hour postdose must be reviewed before receiving the dose of venetoclax for that day. Patients who develop electrolyte changes suggestive of TLS should undergo aggressive management and further monitoring per Appendix 5, Recommendations for Initial Management of Electrolyte Imbalances and Prevention of Tumor Lysis Syndrome.

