**Table 2 Venetoclax Dose Modifications for Non-Hematologic Toxicity**

Non-hematologic Toxicity	
Event(s)	Dose Delay or Modification
Grade 3 or 4 TLS (first episode and subsequent episodes)	

Hold all study treatments (venetoclax) until TLS resolves. The patient's next dose may be delayed for up to 28 days.

Following complete resolution of TLS, if venetoclax was held for 14 days or less, venetoclax may be restarted at the same dose or at one lower dose level as determined by the investigator based on a risk assessment (including tumor burden status) in conjunction with prophylactic hydration and uricosuric agent; hospitalization for restarting the venetoclax dose may be considered at the discretion of the investigator. Dose must be resumed at one lower dose level if interruption lasted more than 14 days.

Grade 3 or 4 non-hematologic toxicity not specifically described above	

Delay venetoclax for a maximum of 28 days.

First episode: If improvement to Grade <math>\leq</math> 1 or baseline, resume previous doses of venetoclax.

For subsequent episodes: If improvement to Grade <math>\leq</math> 1 or baseline, restart venetoclax at one dose level reduction (see Table 3).

Grade 2 non-hematologic toxicity	Delay treatment with venetoclax until resolution to Grade $\leq$ 1 (or baseline status) for a maximum of 28 days. After resolution, resume the full dose of venetoclax.
Grade 1 non-hematologic toxicity	No dose reduction or delay

TLS = tumor lysis syndrome.

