**Table 3 Venetoclax Dose Reduction**

Venetoclax Current Dose Level	Venetoclax Dose Reduction
800 mg	400 mg
400 mg	200 mg
200 mg	100 mg
100 mg	Discontinue venetoclax

Gradual dose increase following resolution of toxicity leading to a dose reduction may be considered if the patient is stable for 2 weeks on the lower dose; however, if the toxicity recurs, the patient may continue treatment on the lower dose.

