Adverse events	Continuous Monitoring																					
Survival visit or phone call													x									

Day *	Screening	Treatment Period									Study Completion/Early Term Visit	Follow-Up (36 mos after enrollment)	
		Cycle 1				Cycles 2 and 3			Cycles 4 - 24			Disease Follow up	Survival Follow up
	-28 to -1	1	2	3	8	15	22	1	15	1	30 days post last dose	Q3 months	

\* All visits +/- 3 days (except for survival follow -up)

a Confirm eligibility criteria; complete eligibility worksheet with PI/Sub I signature

b Heart rate, systolic and diastolic blood pressure and temperature.

c Weight at Cycle 1 Day 1 should be used for dose calculations for all cycles, unless there is a  $\geq$  10% change. If a weight change  $\geq$  10 % occurs, recalculate BSA. Weight should be done every cycle D1.

d Hemoglobin, hematocrit, platelet count, RBC count, WBC count, percent and absolute differential count (neutrophils, bands, eosinophils, lymphocytes, monocytes, basophils, other cells).

e Sodium, potassium, chloride, bicarbonate, glucose, BUN, creatinine, calcium, phosphorus, magnesium, total and direct bilirubin, total protein, albumin, ALT, AST, LDH, alkaline phosphatase, creatinine phosphokinase, and uric acid. During treatment phase, perform mini chem or as clinically indicated.

f All patients must be screened for hepatitis B infection before starting treatment. Carriers of Hep B with active HBV infection should be recommended prophylaxis to prevent reactivation and monitored accordingly for several months after rituximab treatment and should be managed as indicated.

g Only for women of child-bearing potential; Please note that female patients of reproductive potential who are not surgically sterile must practice adequate birth control for a minimum of twelve months post-treatment; male patients who are not surgically sterile must practice adequate birth control for 3 months after venetoclax and 12 months after Rituxan.

h Radiology includes: CT Chest/Abdomen/Pelvis for staging of disease and PET scan; Neck CT to be followed if clinically indicated.

i Perform baseline bone marrow analysis less than or equal to 42 days before first dose of study drug. BM evaluation should also be performed during the study for confirmation of CR within 6 weeks of initial documentation of CR by other assessments for patients with a positive screening bone marrow.

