j Physician will assess disease status post cycle 2, 4, and 6 and then every 3 cycles (+/- 14 days ) until PD, subject withdrawal, death, study is terminated, or until 2 years after the last patient has been enrolled.

k PET and CT (CT neck if clinically indicated at screening) during screening (at baseline) Q2 cycles during treatment (post cycle 2, 4 and 6) – CT and PET to be done separately ; if PET/CT done during screening (at baseline) repeat CT only. PET repeated at time points at investigator's discretion. PET can be repeated to confirm CR if baseline PET was positive.

l - Follow up: During disease follow up, patients will be seen by MD and disease evaluations will be done until PD, subject withdrawal, death, study is terminated or 36 months after enrollment is reached. Survival follow up (after PD), patients will be followed for survival until death or subject withdrawal or study is terminated

m- hematology and complete chemistry as listed in e at 8 hrs (+/- 30 min) and 24 hrs (+/- 2 hrs) post-1st dose of venetoclax.

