**FIRST DOSE OF VENETOCLAX OR DOSE INCREASE**

- Within the first 24 hours after either the first dose or dose increase, if any laboratory criteria below are met, the patient should be hospitalized for monitoring and the investigator notified. No additional GDC-0199 doses should be administered until resolution. A rapidly rising serum potassium level is a medical emergency.
- Nephrology (or acute dialysis service) must be consulted/contacted on admission (per institutional standards to ensure emergency dialysis is available).
- Intravenous (IV) fluids (e.g., D5 1/2 normal saline) should be initiated at a rate of at least 1 mL/kg/h rounded to the nearest 10 mL (target 150 to 200 mL/h; not < 50 mL/h). Modification of fluid rate should also be considered for individuals with specific medical needs.
- Monitor for symptoms or signs of tumor lysis syndrome (TLS; e.g., fever, chills, tachycardia, nausea, vomiting, diarrhea, diaphoresis, hypotension, muscle aches, weakness, paresthesias, mental status changes, confusion, and seizures). If any clinical features are observed, recheck potassium, phosphorus, uric acid, calcium and creatinine within 1 hour.
- Vital signs should be taken at time of all blood draws or any intervention.
- The management recommendations below focus on the minimum initial responses required. If a diagnosis of TLS is established, ongoing intensive monitoring and multi-disciplinary management will be as per institutional protocols.

Abnormality	Management Recommendations
Hyperkalemia (including rapidly rising potassium)	
Potassium $\geq 0.5$ mmol/L increase from prior value (even if potassium within normal limits [WNL])	
 
Recheck potassium, phosphorus, uric acid, calcium, and creatinine in 1 hour. If further <math>\geq 0.2</math> mmol/L increase in potassium, but still <math><</math>ULN, manage as per potassium <math>\geq</math>ULN. Otherwise recheck in 1 hour.
 
Resume per protocol testing if change in potassium is <math>< 0.2</math> mmol/L, and potassium <math><</math>ULN, and no other evidence of tumor lysis
 
At discretion of investigator, may recheck prior to hospitalization. If stable or decreased, and still WNL, hospitalization is at the discretion of the investigator. Potassium, phosphorus, uric acid, calcium, and creatinine must be rechecked within 24 hours.
 

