## ONGOING DOSING OF VENETOCLAX

Management of electrolyte changes from last value at intervals > 24 hours after either the first dose or dose increase (e.g., 48 or 72 hours) are as stated below. Note: If the patient is hospitalized, no additional GDC-0199 doses should be administered until resolution.

- For potassium, admit patient for any increase  $\geq$  1.0 mmol/L (1.0 mEq/L), or any level  $>$  upper limit of normal.
- Refer to the management guidelines for electrolyte changes observed within the first 24 hours after either the first dose or dose increase (table above).
- If a smaller potassium increase is observed that does not meet the criteria for admission above, recheck potassium, phosphorus, uric acid, calcium, and creatinine in 24 hours and confirm no evidence of tumor lysis prior to further GDC-0199 dosing.
- For uric acid, calcium, phosphorus, and creatinine, refer to the management guidelines for electrolyte changes observed within the first 24 hours after either the first dose or dose increase (table above)

Abnormality	Management Recommendations
Creatinine	
Increase $\geq$ 25% from baseline	

• Start or increase rate of IV fluids.

• Recheck potassium, phosphorus, uric acid, calcium, and creatinine in 1 to 2 hours.

IV = intravenous; ULN = upper limit of normal; WNL = within normal limits.

## Appendix 6

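### Timed TLS chemistry is scheduled only for the first venetoclax dose although Appendix 5 sets limits for dose increases, and a patient started below the cohort dose can count toward escalation

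*Combined protocol and SAP*

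**What the plan says.** **TLS chemistry.** On Cycle 1 Day 2, Section 7.1.3 orders vital signs, chemistry and hematology before the first venetoclax dose and "at 8 and 24 hours following the dose". Hospitalized patients have a further TLS sample at 12 hours. Flowchart footnote m agrees: "hematology and complete chemistry as listed in e at 8 hrs (+/- 30 min) and 24 hrs (+/- 2 hrs" after the first dose. Footnote e governs other on-treatment chemistry: "During treatment phase, perform mini chem or as clinically indicated".

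The first part of Appendix 5 opens "Within the first 24 hours after either the first dose or dose increase, if any laboratory criteria below are met" and then calls for hospitalization and no further venetoclax until resolution. Its second part covers "intervals > 24 hours after either the first dose or dose increase".

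Two kinds of later dose matter here:

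- **Re-increase.** The note to Table 3 says: "Gradual dose increase following resolution of toxicity leading to a dose reduction may be considered", once the patient has been stable on the lower dose for two weeks.
- **Restart after Grade 3 or 4 TLS.** After complete resolution and a hold of 14 days or less, Table 2 says "venetoclax may be restarted at the same dose or at one lower dose level as determined by the investigator". This comes with a risk assessment, hydration, a uricosuric agent and optional hospitalization. For longer holds: "Dose must be resumed at one lower dose level if interruption lasted more than 14 days".

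**Lower start.** Under Hospitalization Procedures, Section 7.1.3 lets a patient at particularly high TLS risk begin below the assigned venetoclax dose, after discussion with the medical monitor. Section 5 bases escalation on three cohort subjects who have completed the 28-day DLT window, rules out intrapatient escalation, and wants at least six subjects treated at the MTD or highest tested dose. Section 12 replaces patients for non-compliance, for leaving treatment in Cycle 1 for reasons other than drug-related toxicity, for missing more than four oral doses for reasons other than toxicity, and for stopping rituximab in Cycle 1.

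**The concern.** Appendix 5 states limits for a dose increase, but no part of the schedule produces the values to compare with them. The protocol gives reasons not to rely on symptoms. Section 7.1.3 says chemistry can change within 6 to 8 hours of the first dose, and Section 1.2.4 describes a Grade 4 TLS DLT in a patient with laboratory abnormalities only. TLS is a realistic risk with this combination: Section 12 cites 2 TLS cases in a 24-patient venetoclax and ibrutinib series in mantle cell lymphoma. A patient restarting after Grade 3 or 4 TLS has already shown susceptibility, yet has fewer scheduled post-dose samples than a first-dose patient.

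The lower start bears on the primary objective. In a cohort of three to six, one patient can change the escalation decision. If that patient took less than the cohort dose, the DLT count partly describes a dose not given.

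**Working it through.** **Part 1: limits against schedule.** No arithmetic in the plan bears on this, so the texts are set side by side.

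| Venetoclax dose | Named in Appendix 5's 24-hour limits | Chemistry scheduled before | Chemistry scheduled at 8 h and 24 h |
|---|---|---|---|
| First dose | Yes | Yes | Yes |
| Table 3 re-increase | Yes | No | No |
| Restart after Grade 3 or 4 TLS, same or lower dose | No | Not scheduled, but implied by complete resolution | No |

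Some limits also need a comparator. Potassium is judged on a rise of 0.5 mmol/L from the prior value, phosphorus partly on a rise of 0.5 mg/dL, and one uric acid criterion on creatinine against the pre-dose level.

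Routine chemistry in Appendix 1 does not fill the gap:

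- Cycle 1: Days 1, 2, 3, 8, 15 and 22, then Cycle 2 Day 1 (Day 29). Gaps after Day 3 are 5, 7, 7 and 7 days.
- Cycles 2 and 3: Days 1 and 15, so 14 days apart.
- Cycle 4 onward: 28 days apart. With ±3 days at each visit, 28 − 6 = 22 to 28 + 6 = 34 days.

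Dosing starts on Day 2 and a re-increase needs two stable weeks on a reduced dose, so it cannot come before about the third week. The documents do not say how many patients would re-increase or restart.

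**Part 2: effect of one low-start patient on escalation.** The plan gives no escalation probability to reproduce and no DLT rate for this triplet, so the rates below are assumptions. The rule is from Section 5: escalate on 0/3, or on 1/3 followed by 0/3. The decision concerned is 400 to 800 mg.

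P(escalate) = P(0 of first 3) + P(1 of first 3) × P(0 of next 3)

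Let p = 0.30 at the cohort dose and q = 0.10 at the lower dose.

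- All six at the cohort dose: 0.343 + 0.441 × 0.343 = **0.494**.
- One of the first three at q: P(0/3) = 0.7 × 0.7 × 0.9 = 0.441; P(1/3) = 0.1 × 0.49 + 0.9 × 0.42 = 0.427; 0.441 + 0.427 × 0.343 = **0.587** (+9.3 points).
- One of the second three at q: 0.343 + 0.441 × 0.441 = **0.537** (+4.3 points).

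Range for a patient among the first three:

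| p | q | All at cohort dose | One at lower dose | Change (points) |
|---|---|---|---|---|
| 0.20 | 0.15 | 0.709 | 0.732 | +2.4 |
| 0.40 | 0.05 | 0.309 | 0.444 | +13.5 |
| 0.30 | 0.20 | 0.494 | 0.541 | +4.7 |
| 0.30 | 0.30 | 0.494 | 0.494 | 0 |
| 0.30 | 0.40 | 0.494 | 0.448 | −4.7 |

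The last three rows allow for selection: these patients are chosen for high TLS risk, so their DLT rate at the lower dose may not be low.

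**The case against.** **On the chemistry.** A reader might infer that a patient can be restarted after Grade 3 or 4 TLS with no chemistry at all. The documents do not support that. Table 2 requires complete resolution first, which cannot be judged without the TLS analytes, and Appendix 5 bars further dosing until resolution. A reader might also take the Appendix 5 limits for a dose increase to govern restarts. They do not, because a restart at the same or a lower dose is not an increase. Nor are the 14-day and 28-day gaps the whole picture: a TLS after the first dose, held for 14 days or less, would restart within the roughly weekly Cycle 1 schedule. The re-increase is optional, gradual and preceded by two stable weeks, prior exposure may lower the risk, and chemistry may be drawn when clinically indicated. All of this stands and keeps the point small. It does not supply a scheduled value before or after a re-increase, or after a restart.

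**On the lower start.** A reader might infer that such a patient also fills one of the six places behind the MTD. Section 5 wants at least six subjects treated at that dose, and Section 5.2 says each cohort receives its assigned dose. That wording points against counting the patient, so for the MTD the text is unclear rather than wrong. It does not settle the escalation step, which rests on completing the window.

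A reader might further infer that the trial will escalate too readily. The direction is not established, and every figure is conditional on an uncommon event whose frequency is unknown. The expansion stopping rule gives partial later protection. With boundaries 3/5, 4/11, 5/17 and 6/24, its exact crossing probability at a 30% toxicity rate is 0.7996, matching the 0.800 in Section 12, so it misses about 1 in 5.

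**Conclusion.** Both parts hold in limited form, and together they make a cheap improvement.

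1. A Table 3 re-increase has no scheduled chemistry before or after it, although Appendix 5 sets 24-hour limits for it. A restart after Grade 3 or 4 TLS lacks scheduled post-dose chemistry only. Few patients are likely to be affected.
2. A DLT-free patient started below the cohort dose can, as written, count toward escalation. At the assumed 30% and 10%, this adds 9.3 points among the first three or 4.3 among the second three. For a patient among the first three, the gain is 2 to 14 points over cohort-dose rates of 20% to 40% and lower-dose rates of 5% to 15%. It is zero or negative if selection for TLS risk brings the patient's DLT rate up to or above the cohort rate.

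The reading of the text is firm. The sizes in part 2 rest wholly on assumed rates.

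**What to change.** **Chemistry.** Extend Section 7.1.3 and footnote m so that potassium, phosphorus, uric acid, calcium and creatinine are drawn pre-dose and at 8 and 24 hours for every venetoclax dose increase and every restart after Grade 3 or 4 TLS, at the same or a lower dose. Cost: amendment wording and a few blood draws in a few patients.

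**DLT evaluability.** In Sections 5 and 12, state that an escalation-phase patient started below the cohort's venetoclax dose for non-toxicity reasons, with no DLT, is not DLT-evaluable at that level and is replaced, while any DLT in such a patient still counts. Cost: amendment wording and possibly one replacement patient.

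The second rule leans cautious. At the assumed rates, with the replacement at full dose, a first-three place so filled has DLT probability 0.10 + 0.90 × 0.30 = 0.37. Then P(0/3) = 0.49 × 0.63 = 0.309, P(1/3) = 0.37 × 0.49 + 0.63 × 0.42 = 0.446, and P(escalate) = 0.309 + 0.446 × 0.343 = 0.462, about 3 points below the 0.494 with all patients at dose. That is an acceptable price for not overlooking a DLT.

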## ONGOING DOSING OF VENETOCLAX

Management of electrolyte changes from last value at intervals > 24 hours after either the first dose or dose increase (e.g., 48 or 72 hours) are as stated below. Note: If the patient is hospitalized, no additional GDC-0199 doses should be administered until resolution.

- For potassium, admit patient for any increase  $\geq$  1.0 mmol/L (1.0 mEq/L), or any level  $>$  upper limit of normal.
- Refer to the management guidelines for electrolyte changes observed within the first 24 hours after either the first dose or dose increase (table above).
- If a smaller potassium increase is observed that does not meet the criteria for admission above, recheck potassium, phosphorus, uric acid, calcium, and creatinine in 24 hours and confirm no evidence of tumor lysis prior to further GDC-0199 dosing.
- For uric acid, calcium, phosphorus, and creatinine, refer to the management guidelines for electrolyte changes observed within the first 24 hours after either the first dose or dose increase (table above)

Abnormality	Management Recommendations
Creatinine	
Increase $\geq$ 25% from baseline	

• Start or increase rate of IV fluids.

• Recheck potassium, phosphorus, uric acid, calcium, and creatinine in 1 to 2 hours.

IV = intravenous; ULN = upper limit of normal; WNL = within normal limits.

## Appendix 6

### The Lugano Classification for Response Assessment of Non-Hodgkin Lymphoma

Response and Site	PET-CT-Based Response	CT-Based Response
Complete		
Lymph nodes and extralymphatic sites	Complete metabolic response Score 1, 2, or 3* with or without a residual mass on 5PS† It is recognized that in Waldeyer's ring or extranodal sites with high physiologic uptake or with activation within spleen or marrow (eg, with chemotherapy or myeloid colony-stimulating factors), uptake may be greater than normal mediastinum and/or liver. In this circumstance, complete metabolic response may be inferred if uptake at sites of initial involvement is no greater than surrounding normal tissue even if the tissue has high physiologic uptake	Complete radiologic response (all of the following) Target nodes/nodal masses must regress to $\leq 1.5$ cm in LDi No extralymphatic sites of disease
Nonmeasured lesion	Not applicable	Absent
Organ enlargement	Not applicable	Rgress to normal
New lesions	None	None
Bone marrow	No evidence of FDG-avid disease in marrow	Normal by morphology; if indeterminate, IHC negative
Partial		
Lymph nodes and extralymphatic sites	Partial metabolic response Score 4 or 5† with reduced uptake compared with baseline and residual mass(es) of any size At interim, these findings suggest responding disease  At end of treatment, these findings indicate residual disease	Partial remission (all of the following) $\geq 50\%$ decrease in SPD of up to 6 target measurable nodes and extranodal sites When a lesion is too small to measure on CT, assign 5 mm $\times$ 5 mm as the default value When no longer visible, 0 $\times$ 0 mm For a node $> 5$ mm $\times$ 5 mm, but smaller than normal, use actual measurement for calculation Absent/normal, regressed, but no increase Spleen must have regressed by $> 50\%$ in length beyond normal
Nonmeasured lesions	Not applicable	None
Organ enlargement	Not applicable	Not applicable
New lesions	None	
Bone marrow	Residual uptake higher than uptake in normal marrow but reduced compared with baseline (diffuse uptake compatible with reactive changes from chemotherapy allowed). If there are persistent focal changes in the marrow in the context of a nodal response, consideration should be given to further evaluation with MRI or biopsy or an interval scan	
No response or stable disease		
Target nodes/nodal masses, extranodal lesions	No metabolic response Score 4 or 5 with no significant change in FDG uptake from baseline at interim or end of treatment	Stable disease $< 50\%$ decrease from baseline in SPD of up to 6 dominant, measurable nodes and extranodal sites; no criteria for progressive disease are met
Nonmeasured lesions	Not applicable	No increase consistent with progression
Organ enlargement	Not applicable	No increase consistent with progression
New lesions	None	None
Bone marrow	No change from baseline	Not applicable
Progressive disease		
Individual target nodes/nodal masses	Progressive metabolic disease Score 4 or 5 with an increase in intensity of uptake from baseline and/or	Progressive disease requires at least 1 of the following PPD progression:
Extranodal lesions	New FDG-avid foci consistent with lymphoma at interim or end-of-treatment assessment	An individual node/lesion must be abnormal with: LDi $> 1.5$ cm and Increase by $\geq 50\%$ from PPD nadir and An increase in LDi or SDi from nadir 0.5 cm for lesions $\leq 2$ cm 1.0 cm for lesions $> 2$ cm In the setting of splenomegaly, the splenic length must increase by $> 50\%$ of the extent of its prior increase beyond baseline (eg, a 15-cm spleen must increase to $> 16$ cm). If no prior splenomegaly, must increase by at least 2 cm from baseline New or recurrent splenomegaly New or clear progression of preexisting nonmeasured lesions
Nonmeasured lesions	None	

Response and Site	PET-CT-Based Response	CT-Based Response
New lesions	New FDG-avid foci consistent with lymphoma rather than another etiology (eg, infection, inflammation). If uncertain regarding etiology of new lesions, biopsy or interval scan may be considered	Regrowth of previously resolved lesions A new node > 1.5 cm in any axis A new extranodal site > 1.0 cm in any axis; if < 1.0 cm in any axis, its presence must be unequivocal and must be attributable to lymphoma Assessable disease of any size unequivocally attributable to lymphoma
Bone marrow	New or recurrent FDG-avid foci	New or recurrent involvement

Abbreviations: 5PS, 5-point scale; CT, computed tomography; FDG, fluorodeoxyglucose; IHC, immunohistochemistry; LDi, longest transverse diameter of a lesion; MRI, magnetic resonance imaging; PET, positron emission tomography; PPD, cross product of the LDi and perpendicular diameter; SDi, shortest axis perpendicular to the LDi; SPD, sum of the product of the perpendicular diameters for multiple lesions.

\*A score of 3 in many patients indicates a good prognosis with standard treatment, especially if at the time of an interim scan. However, in trials involving PET where de-escalation is investigated, it may be preferable to consider a score of 3 as inadequate response (to avoid undertreatment). Measured dominant lesions: Up to six of the largest dominant nodes, nodal masses, and extranodal lesions selected to be clearly measurable in two diameters. Nodes should preferably be from disparate regions of the body and should include, where applicable, mediastinal and retroperitoneal areas. Non-nodal lesions include those in solid organs (eg, liver, spleen, kidneys, lungs), GI involvement, cutaneous lesions, or those noted on palpation. Nonmeasured lesions: Any disease not selected as measured, dominant disease and truly assessable disease should be considered not measured. These sites include any nodes, nodal masses, and extranodal sites not selected as dominant or measurable or that do not meet the requirements for measurability but are still considered abnormal, as well as truly assessable disease, which is any site of suspected disease that would be difficult to follow quantitatively with measurement, including pleural effusions, ascites, bone lesions, leptomeningeal disease, abdominal masses, and other lesions that cannot be confirmed and followed by imaging. In Waldeyer's ring or in extranodal sites (eg, GI tract, liver, bone marrow), FDG uptake may be greater than in the mediastinum with complete metabolic response, but should be no higher than surrounding normal physiologic uptake (eg, with marrow activation as a result of chemotherapy or myeloid growth factors).

†PET 5PS: 1, no uptake above background; 2, uptake ≤ mediastinum; 3, uptake > mediastinum but ≤ liver; 4, uptake moderately > liver; 5, uptake markedly higher than liver and/or new lesions; X, new areas of uptake unlikely to be related to lymphoma.

